Evaluation of the Effectiveness Delirium Preventive Care Protocol For Hip Fracture Patients

NCT 04188795

Document Date: January 10, 2019

STUDY PROTOCOL WITH ANALYSIS PLAN

Hip fracture, which is defined as the most serious outcome of osteoporosis, affects patients' daily activities and quality of life (Ensrud, 2013). A high prevalence for the development of delirium after hip fracture is found in the group of geriatric patients (Tsang et al., 2012). Delirium prevention is essential rather than treatment (Strijbos et al., 2013). According to The National Institute for Health and Clinical Excellence (NICE), 30% of delirium cases can be prevented (NICE, 2010). The prevention of delirium, which is a multifactorial phenomenon, can be achieved through a multicomponent care protocol that targets at specific risk factors for delirium.

The aim of this study was to investigate the effectiveness of delirium preventive care protocol on pain, functional status, sleep quality and delirium prevention in patients with hip fracture.

This prospective, randomized controlled experimental study was conducted at a training and research hospital's orthopedics and traumatology department in Turkey. Hip fracture patients aged ≥ 65 years who were underwent surgery were included. The sample included 40 patients from the intervention group and 40 from the control group. A protocol with a nursing care plan referenced from international guideline and other literature was developed to prevent delirium and applied to intervention group (SIGN, 2008; NICE, 2010, Moon & Lee, 2010; Bjorkelund et al, 2010). Control group was applied to regular nursing care in line with the clinical procedure. Study data was collected by using Patient Information Form, Confusion Assessment Method, Visual Analogue Scale, Barthel Index, Mini Nutritional Assessment-Short Form and Richards Campbell Sleep Questionnaire.

Delirium preventive care protocol applied to the intervention group includes; psychosocial care, monitor oxygen saturation to prevent hypoxemia, prevention dehydration and nutritional support, normal elimination, adequate pain relief, sleep management, remove unnecessary catheter and early mobilization.

The data obtained from the study were analyzed using the SPSS version 22.00 software package. Kolmogorov Smirnov and Shapiro Wilk tests were used to evaluate the data with normal or non-normal distribution. Number, percentage, mean, standard deviation, median values and interquartile range were used in descriptive statistical evaluation of the data. In terms of the continuous variables of the intervention and control groups, the significance test of the difference between the two means, which is the parametric test for the normal distribution values (Student's t Test), and the Mann-Whitney U Test for the values that do not fit the normal distribution were used. Pearson chi-square test was used to analyze categorical variables. Fisher's chi-square test was used when the expected value was less than five. ANOVA test was used for the evaluation of normal preoperative, postoperative 1st day and pre-discharge data. Two groups t-test (Paired Sample t test) was used for comparisons

between groups. Friedman test and Wilcoxon test were used for the evaluation of preoperative, postoperative 1st day and pre-discharge data that do not conform to normal distribution. Cronbach α coefficient was used to evaluate the reliability of RCSQ sleep scale. $p < 0.05$ was considered statistically significant and $p < 0.001$ was considered statistically highly significant.

References:

1. Ensrud, K. E. (2013). Epidemiology of fracture risk with advancing age. *J Gerontol A Biol Sci Med Sci*, 68(10), 1236-1242.
2. Tsang, L. F., Yeung, C. H., Tse, C. C., Lam, K. B., Cheung, L. P., Chu, K. K., ... & Lau, P. Y. (2012). Developing a predictive tool for post-operative delirium in orthopaedic settings in Hong Kong. *International Journal of Orthopaedic and Trauma Nursing*, 16(3), 147-159.
3. Strijbos, M. J., Steunenberg, B., van der Mast, R. C., Inouye, S. K., & Schuurmans, M. J. (2013). Design and methods of the Hospital Elder Life Program (HELP), a multicomponent targeted intervention to prevent delirium in hospitalized older patients: efficacy and cost-effectiveness in Dutch health care. *BMC geriatrics*, 13(1), 78.
4. Scottish Standards of Care for Hip Fracture Patients 2016. https://www.shfa.scot.nhs.uk/_docs/20161109_SSC_for_Hip_Fracture_Patients.pdf. Date: 01.09.2018.
5. The management of hip fracture in adults. Methods, Evidence & Guidance. (Updated 2017). <https://www.nice.org.uk/guidance/cg124/evidence/full-guideline-pdf-183081997>. Date: 01.09.2018.

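### The tests named for comparing the arms on continuous scores leave out the preoperative score, which can cost power; the loosely defined normality rule matters less

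*Combined protocol and SAP*

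**What the plan says.** The relevant text is the statistical analysis paragraph of the combined protocol and SAP. It opens the choice of test with "Kolmogorov Smirnov and Shapiro Wilk tests were used to evaluate the data with normal or non-normal distribution". Scores judged normal are compared between arms by Student's t test; for the rest, "the Mann-Whitney U Test for the values that do not fit the normal distribution were used". No covariate is named for either. The paragraph does not say which normality test prevails, at what level, or whether it is applied to each arm, to all 80 patients or to each visit.

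The repeated measurements are handled separately. For normal data, "ANOVA test was used for the evaluation of normal preoperative, postoperative 1st day and pre-discharge data"; for other data, "Friedman test and Wilcoxon test were used for the evaluation of preoperative, postoperative 1st day and pre-discharge data". No group term or group-by-time term is stated for either.

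Between these two sentences stands "Two groups t-test (Paired Sample t test) was used for comparisons", which runs over a page break and says that the comparisons are between groups.

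The design description adds that "The sample included 40 patients from the intervention group and 40 from the control group" and that the care protocol "was developed to prevent delirium and applied to intervention group". It gives no start time for that protocol relative to the preoperative assessment. It also does not say which scales were scored before surgery.

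**The concern.** Three of the four targets in the stated aim (pain, functional status and sleep quality) are scale scores. If a patient's score before surgery predicts the score afterwards, a comparison of arms that ignores it carries avoidable variance. With 40 patients per arm that can matter, and using a score already collected needs no extra data.

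The choice between a mean-based and a rank-based test is also left until the data are seen, with two gatekeeping tests and no rule for when they disagree. That leaves the analyst some discretion, and no common effect measure is required across visits. The paired t test sentence, read literally, applies a paired test to two independent arms and conflicts with the Student's t test already named.

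Delirium analysed as yes/no goes to the chi-square or Fisher test and is not affected.

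**Working it through.** **Inputs.** From the document: 40 per arm and a 0.05 significance threshold. Assumed, because the document gives none of them: two-sided testing, an effect of d = 0.5 SD, the correlation r between preoperative and later scores, and all distribution shapes. The document gives no basis for 40 per arm, so there is no sample size calculation to reproduce. For orientation, 40 per arm detects d = (1.960 + 0.842) × √(2/40) = 0.63 SD with 80% power.

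**Power with and without the preoperative score.** Approximate power is Φ(d / (s × √(2/40)) − 1.960). Here s = 1 for a follow-up-only comparison and s = √(1 − r²) for ANCOVA. With d = 0.5, d/√(2/40) = 0.5/0.2236 = 2.236.

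- Unadjusted: Φ(2.236 − 1.960) = 61%.
- r = 0.3: s = √0.91 = 0.954; Φ(2.344 − 1.960) = 65%.
- r = 0.5: s = √0.75 = 0.866; Φ(2.582 − 1.960) = 73%.
- r = 0.7: s = √0.51 = 0.714; Φ(3.131 − 1.960) = 88%.

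Simulation with normal scores gives slightly lower figures, which are the ones used in the conclusion: 60% unadjusted against 63%, 72% and 87%. At r = 0.1 and 0.2 it gives about 60% and 61–62%, so essentially nothing is gained. In patient numbers, 40/(1 − r²) shows that adjusting 40 per arm is worth about 44, 53 and 78 unadjusted patients per arm at r = 0.3, 0.5 and 0.7.

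**Why the timing of the preoperative score matters.** If the care protocol had already moved that score by δ, ANCOVA estimates d − rδ. For an assumed δ of 0.15 to 0.25 SD, this runs from 0.50 − 0.3 × 0.15 = 0.455 down to 0.50 − 0.7 × 0.25 = 0.325 SD. Simulated power is then 47–67%, partly below the unadjusted test.

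**How much the normality rule matters.** Simulated trials of 40 + 40 used ten assumed shapes: normal, bounded, stepped and skewed.

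- In single samples of 40, the two normality tests disagree in 5–6% of near-normal cases, and in 30–43% for gamma shape 4 or a whole-number 0–10 scale.
- At a 0.5 SD shift, t and Mann-Whitney reach different significance verdicts in 5–7% of trials with near-normal or bounded scores, and in 11–26% with gamma shapes 4 to 1.
- Precedence matters only when both happen in the same trial. At a 0.5 SD shift with the gate applied per arm, that occurred in 0.1–2.9% of trials. At gamma shape 1, where verdicts differ most, the normality tests disagree in under 1%.
- Type I error is 4.6–5.5% if the rule is followed mechanically under any of four tie-breaks, and 5.6–6.7% if the better p-value is kept.

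The 3% ceiling covers precedence only. Whether the gate is applied per arm or to the pooled 80 is a separate gap. With Shapiro-Wilk at 5%, the two units pick different tests in 7–38% of data sets at one visit. How often that also changes the conclusion was not counted, but it cannot exceed the rate at which t and Mann-Whitney verdicts differ.

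**The case against.** The strongest reply is that the ANOVA over three time points may have been meant as a group-by-time model, which would bring in the preoperative score. That is possible: no group term is stated, but none is excluded. So a reader might infer that the plan discards the preoperative data, and the document does not support that. It shows only that the tests clearly assigned to comparing the arms do not use those data. Even a group-by-time contrast would act like a change from baseline, with s = √(2 − 2r). The power formula then gives 47%, 61% and 82% at r = 0.3, 0.5 and 0.7, below ANCOVA each time.

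A reader might also infer that the normality gate makes the results untrustworthy or inflates false positives. The figures above do not bear that out. The gate even has a merit: on strongly skewed scores it keeps most of Mann-Whitney's power advantage. Imposing a mean-based analysis on every scale is therefore a trade-off.

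Finally, a reader might infer that a paired test was run across the arms. Its place after ANOVA, parallel to Wilcoxon after Friedman, makes a slip for pairs of visits within patients more likely. The sentence needs correcting either way but adds little weight.

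It also stands that the power gain depends on an unknown correlation, and that the document names no primary outcome or time point, which leaves more discretion than the choice between two normality tests.

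**Conclusion.** The point holds as a missed gain in efficiency and a gap in specification; it does not threaten validity. As written, the between-arm tests for continuous scores do not use the preoperative score. At 40 per arm and an assumed 0.5 SD effect with near-normal scores, adjustment would add about 3, 12 and 27 percentage points to a power of about 60% at baseline correlations of 0.3, 0.5 and 0.7. It would add almost nothing at 0.1 to 0.2. This rests on a preoperative score existing for the scale and being taken before the care protocol began; the document confirms neither.

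The textual gap is certain. The magnitudes are illustrative, because effect size, correlation and shapes are all assumed. The missing precedence between normality tests is detail to be filled in. The change is worth making.

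**What to change.** - **Scales with a valid preoperative score.** For each of pain, function and sleep scored before the care protocol starts, name one baseline-adjusted between-group analysis in advance (ANCOVA or a mixed model). Report the adjusted difference with a robust or bootstrap 95% CI. Use it for both the postoperative day 1 and the pre-discharge scores, whatever the normality tests show, with Mann-Whitney as the sensitivity analysis. A rank-based ANCOVA may be named in advance for a scale expected to be strongly skewed.
- **Scales without one.** Name one unadjusted test per scale in advance. State for each scale which case applies.
- **Paired t test sentence.** It cannot compare two independent arms. If it means pairs of visits within patients, say so.
- **Timing.** The paragraph is in the past tense ("The data obtained from the study were analyzed using the SPSS version 22.00 software package"). If the analysis is done, report this as a re-analysis that was not pre-specified.

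**Cost.** No new data are needed: either a change of wording or one re-analysis. The drawback is that a mean-based primary analysis loses power on strongly skewed scores under a shift: about 60% against 74% for Mann-Whitney at gamma shape 2 and 0.5 SD. The ranking reverses for a multiplicative effect (71% against 64% at the same shape and a ratio of 1.5). There is little to gain if the baseline correlation is below about 0.3.

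### Continuous outcomes are compared between arms without using the preoperative values, which can cost precision, and a paired t test is assigned to comparisons between independent groups

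*Combined protocol and SAP*

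**What the plan says.** The document has no numbered sections; the points below come from its study design paragraph and its statistical analysis paragraph.

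- **Aims.** The study is to assess the "effectiveness of delirium preventive care protocol on pain, functional status, sleep quality and delirium prevention in patients with hip fracture". Three of these four aims (pain, function and sleep) can be measured on continuous scales. This point does not concern delirium.
- **Design.** The trial is randomised, and "The sample included 40 patients from the intervention group and 40 from the control group". No matching of patients is described.
- **Between-arm test.** "In terms of the continuous variables of the intervention and control groups, the significance test of the difference between the two means" is given as Student's t test, and "the Mann-Whitney U Test for the values that do not fit the normal distribution were used". No ANCOVA, regression, mixed model or other baseline adjustment is named.
- **Serial data.** "ANOVA test was used for the evaluation of normal preoperative, postoperative 1st day and pre-discharge data". Friedman and Wilcoxon tests are named for the non-normal case. No arm factor or arm-by-time term is mentioned, and the scales measured before surgery are not listed.
- **Paired test.** "Two groups t-test (Paired Sample t test) was used for comparisons"; the sentence then runs over a page break and says that these comparisons are between groups.

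**The concern.** A preoperative measurement that correlates with the later one explains part of the variation between patients. An analysis that ignores it gives a wider confidence interval than the same patients could have provided. With 80 patients and three continuous aims, this could be material: an assumed true effect of half an SD would be missed about 40% of the time.

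The second issue is a rule that is wrong as written. A paired t test needs natural pairs, and two independently randomised arms have none. If it were applied to the arms, the result would depend on the order in which patients happened to be listed. The wording also places a second test beside Student's t as a comparison of groups, and the type of ANOVA is left open.

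**Working it through.** **Inputs.** From the document: 40 patients per arm and a significance level of 0.05. Assumed, because the document does not give them: two-sided testing, a true difference of 0.4 to 0.6 SD, and a correlation ρ of 0.1 to 0.7 between the preoperative and later values. The plan states no power or sample-size figure, so there is none to reproduce.

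**Unadjusted t test.** SE = SD × √(2/40) = 0.2236 SD, with 78 df and critical value 1.991. For 0.5 SD the noncentrality is 0.5/0.2236 = 2.236, and power from the noncentral t distribution is 59.8%. The 95% CI half-width is 1.991 × 0.2236 = 0.445 SD.

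**ANCOVA on the preoperative value.** SE² = SD² × (2/40) × (1 − ρ²) × (1 + 1/76), with 77 df. The last factor is the expected penalty for estimating the baseline slope. Example at ρ = 0.5: 0.75 × 1.0132 = 0.760; SE = √(0.05 × 0.760) = 0.195 SD; noncentrality 0.5/0.195 = 2.565; power 71.7%.

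| | Unadjusted | ρ 0.1 | ρ 0.3 | ρ 0.5 | ρ 0.7 |
|---|---|---|---|---|---|
| Variance factor | 1 | 1.003 | 0.922 | 0.760 | 0.517 |
| Power at 0.4 SD | 42.4% | 42.2% | 45.2% | 52.7% | 69.1% |
| Power at 0.5 SD | 59.8% | 59.7% | 63.3% | 71.7% | 86.7% |
| Power at 0.6 SD | 75.5% | 75.4% | 78.8% | 86.0% | 95.8% |
| Difference detectable at 80% power (SD) | 0.634 | 0.635 | 0.609 | 0.553 | 0.456 |
| 95% CI half-width (SD) | 0.445 | 0.446 | 0.428 | 0.388 | 0.320 |

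Dividing 40 by the variance factor gives the unadjusted arm size with the same variance: at ρ = 0.5, 40/0.760 ≈ 53 per arm.

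**Break-even.** ANCOVA and unadjusted power at 0.5 SD are equal at ρ = 0.115. At ρ = 0 the SE is √(0.05 × 1.0132) = 0.225 SD and power is 59.2%, so the most that needless adjustment costs here is about 0.6 of a power point.

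**Simulation with normal data** (40,000 trials, 0.5 SD). ANCOVA power was 59.5%, 63.3%, 71.6% and 86.9% at the four correlations, against 59.6–60.1% unadjusted. Type I error was 4.9–5.1%.

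**Simulation with bounded data** (20,000 trials; assumed 0–100 scale in steps of 5 with a ceiling, latent mean 85, SD 25). Mann-Whitney power was 53% throughout. ANCOVA gave 52%, 54%, 61% and 75%; rank-based ANCOVA gave 54%, 55%, 62% and 75%. Type I error was 4.9–5.3%.

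**Paired t test taken literally on the two arms.** The SE is the same but there are 39 df (critical value 2.023), so power at 0.5 SD is 58.7% against 59.8%. Simulated type I error was 5.05%. Re-pairing the same data at random changed the significance verdict in about 7% of 20,000 simulated trials.

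**The case against.** The strongest reply is that nothing named for the between-arm comparison is invalid. Student's t and Mann-Whitney are correct for two randomised arms, and adjustment only adds efficiency. The size of that gain rests on a correlation the document does not give: at 0.3 it is 3.5 power points, and at 0.1 it is nil. All of this stands, and it is why the point is about precision only.

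It can also be said that no outcome is shown to qualify. The document does not list the scales measured before surgery or say when the care protocol starts. If the protocol began before the preoperative assessment, that value is not a baseline. This stands too, and the change proposed below is conditional on it.

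On the paired test, the plan expressly gives Student's t or Mann-Whitney to the two arms. The paired test follows the sentence on three time points, just as Wilcoxon accompanies Friedman. The likely intent is therefore comparison between times within an arm. That is a fair reading, but it is not what the sentence says.

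Finally, the ANOVA might include an arm factor and so use the preoperative data between arms. The text does not say so, and Friedman, its non-normal counterpart, points to a within-arm analysis. This is a reason to specify the model.

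**Conclusion.** The concern holds, as something the plan should change rather than a threat to validity. The only between-arm tests clearly named for continuous outcomes are unadjusted, although preoperative values exist for at least some of them. The loss ranges from nothing at a correlation near 0.1 to about 12 power points at 0.5 (71.7 − 59.8) and 27 at 0.7 (86.7 − 59.8), for an assumed 0.5 SD difference. Those figures rest on assumed correlations and effect sizes, two-sided 5% testing, and a preoperative value taken before the care protocol began.

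The paired-test sentence is wrong as written. Followed literally, it would cost about one power point, leave type I error at 5%, and make the result depend on an arbitrary pairing. It is best treated as a labelling error to correct.

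**What to change.** 1. For each continuous outcome with a preoperative value taken before the care protocol starts, make the between-arm analysis an ANCOVA on that value at day 1 and at pre-discharge. Report the adjusted difference with its 95% CI.
2. Where data are clearly non-normal, add a rank-based ANCOVA as a sensitivity analysis.
3. Where no such value exists, or it was taken after the care protocol began, keep Student's t or Mann-Whitney.
4. List the scales measured preoperatively and say when that was done relative to the start of the care protocol.
5. Reassign the paired t test to comparisons between times within an arm, and specify the ANOVA across times as repeated-measures.
6. State that conclusions on effectiveness rest on the between-arm comparison and that within-arm tests are descriptive.

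The cost is wording and a standard model in the software already named; no extra patients or data are needed. One caution is that the analysis paragraph is in the past tense ("The data obtained from the study were analyzed using the SPSS version 22.00 software package"). If the analyses had already been run, the ANCOVA should be reported beside the unadjusted result and labelled as added and not prespecified.

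### The three-time-point tests contain no arm term and the between-arm test ignores the preoperative value, so the planned time analyses do not address the stated aim

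*Combined protocol and SAP*

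**What the plan says.** All references are to the single combined protocol and SAP, which has no numbered sections.

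- **Aim paragraph.** The study is to "investigate the effectiveness of delirium preventive care protocol on pain, functional status, sleep quality and delirium prevention in patients with hip fracture". Except for delirium, these outcomes are naturally measured on scales, and effectiveness is a question about the difference between arms.
- **Design paragraph.** The trial is randomised, and "The sample included 40 patients from the intervention group and 40 from the control group". No matching of patients across arms is described.
- **Statistical analysis paragraph, arm comparison.** "In terms of the continuous variables of the intervention and control groups, the significance test of the difference between the two means" is tested by Student's t, or by Mann-Whitney when the data are not normal. No time point is named and no adjustment for the preoperative value is mentioned.
- **Same paragraph, time comparison.** "ANOVA test was used for the evaluation of normal preoperative, postoperative 1st day and pre-discharge data". The next sentence reads "Two groups t-test (Paired Sample t test) was used for comparisons" and, after a line break, continues "between groups. Friedman test and Wilcoxon test were used for the evaluation of preoperative, postoperative 1st day and pre-discharge data". So the paired t test is assigned to comparisons between groups, and Friedman and Wilcoxon cover the non-normal case.
- **Not stated.** Whether the ANOVA is one-way or repeated-measures, whether it has an arm factor, how sphericity is handled, and whether the pairwise tests depend on a significant overall test or are corrected. The significance threshold is 0.05, with 0.001 labelled highly significant.

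**The concern.** A test of change over time answers whether scores moved between surgery and discharge. After a hip fracture operation, pain, function and sleep can be expected to move in both arms, so a significant time effect is not evidence for the care protocol. With separate time tests in each arm, the natural but mistaken step is to compare their p-values: significant in one arm, not in the other, therefore the protocol works.

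The tests that do compare the arms leave the preoperative value unused, although preoperative data are among those to be analysed. That costs precision in a trial with 40 patients per arm.

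The paired-test sentence is a separate defect. Two independently randomised arms have no natural pairs. If the sentence is followed literally, the result depends on the order in which patients happen to be listed, and the test cannot be run at all once the arms differ in size.

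**Working it through.** The plan gives no effect size, SD, within-patient correlation or power, so there is no figure of its own to reproduce.

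**Inputs.** From the documents: 40 per arm, three time points, threshold 0.05. Assumed: two-sided testing, normal data with equal SD at each time, complete data, and within-patient correlation ρ of 0.3, 0.5 or 0.7.

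**1. Comparing within-arm p-values when the arms do not differ.** Let both arms truly change by 0.4 SD between two time points. The SD of a within-patient difference is √(2(1−ρ)), and the non-centrality of the paired t test (39 df) is 0.4/√(2(1−ρ)) × √40. If P is the power in one arm, the chance that exactly one of two independent arms is significant is 2P(1−P).

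| ρ | SD of difference | Non-centrality | P | 2P(1−P) |
|---|---|---|---|---|
| 0.3 | 1.183 | 2.138 | 0.550 | 49.5% |
| 0.5 | 1.000 | 2.530 | 0.694 | 42.5% |
| 0.7 | 0.775 | 3.266 | 0.890 | 19.6% |

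Simulation gave 49%, 43% and 19%, which agrees to within a percentage point. The true difference between arms is zero in every row.

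**2. What the unused preoperative value is worth.** Take a between-arm effect of 0.5 SD (assumed) at one postoperative time. Unadjusted, the non-centrality is 0.5/√(2/40) = 2.236, and power on 78 df is 60%. Adjusting for the preoperative value multiplies the residual SD by √(1−ρ²) and leaves 77 df.

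| ρ | √(1−ρ²) | Non-centrality | Power |
|---|---|---|---|
| 0.3 | 0.954 | 2.344 | 64% |
| 0.5 | 0.866 | 2.582 | 72% |
| 0.7 | 0.714 | 3.131 | 87% |

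**3. The paired t test between arms.** With 40 arbitrary pairs the test has 39 df instead of 78. In simulation with an assumed 0.6 SD difference, power was 74.5% for the paired test and 75.6% for the independent test. The power loss is small. The defect is that no pairing is defined, so the p-value is not determined by the data alone.

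**4. What depends on the unstated details.** Simulation of one arm of 40 with no true change (40,000 runs):

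- If the ANOVA were one-way, type I error would be 1.5% and 0.3% at ρ = 0.3 and 0.5, and below 0.02% at ρ = 0.7.
- If it is repeated-measures, type I error is about 5% under sphericity, and 6.5% to 6.6% uncorrected in two non-spherical examples.
- Three paired t tests run without a gate have a family-wise error of about 12.5% per scale and arm. Run only after a significant repeated-measures ANOVA, it is about 5% under sphericity. With a Bonferroni threshold of 0.0167 each, it is about 4.4% to 4.6%.

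**The case against.** The strongest reply is that the plan does compare the arms. Student's t and Mann-Whitney are named for that purpose, and in a randomised trial an unadjusted comparison at a follow-up time is a valid test of treatment. This stands: the aim is not left untested. What remains is that the comparison names no time point, ignores the preoperative value, and sits beside time tests that a reader could mistake for evidence of effect.

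It may also be said that the ANOVA could have included arm as a factor. The text names none, and the Friedman and Wilcoxon tests given for the same data when non-normal have no place for one.

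A reader might go further and infer that the longitudinal p-values are wrong in both directions: too conservative because the ANOVA ignores repeated measurement, and too liberal because the pairwise tests are uncorrected. The documents do not support that. They never say the ANOVA is one-way, and its company with the paired t and Friedman tests makes repeated measures the likelier reading. They are silent on gating, which is not the same as saying that the pairwise tests were run ungated. With three time points, pairwise tests that follow a valid overall test hold about 5% under sphericity. Each single paired p-value is valid on its own.

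Finally, the between-groups wording may be a slip for between time points. That is plausible, but the sentence still needs correcting.

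**Conclusion.** The point holds in this form. The tests named for the three-time-point data carry no arm term and cannot show the care protocol's effect. The only between-arm test of continuous variables is unadjusted. The paired t test is literally assigned to a comparison for which no pairs exist.

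Contrasting within-arm results would suggest a difference that is not there in roughly 20% to 50% of trials, for an assumed common change of 0.4 SD and correlations from 0.7 down to 0.3. Adjustment would add about 4 to 27 percentage points of power (64 − 60 to 87 − 60) for an assumed 0.5 SD effect. All of these sizes rest on assumed correlations and effects, because the documents give none.

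The ANOVA type, sphericity handling and gating rule are missing detail. The one-way error rates and the family-wise error of about 12.5% apply only if the plan was carried out in those particular ways, and the text does not say that it was. The change is a worthwhile improvement at low cost; it does not rest on a finding that the planned between-arm test is invalid.

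**What to change.** For each continuous scale measured at all three times (the plan should say which these are), make the between-arm comparison with a linear mixed model for repeated measures. The outcomes are the postoperative day 1 and pre-discharge values. The terms are arm, time, arm-by-time and the preoperative value, with unstructured covariance within patient. Report the between-arm difference at each time with a 95% CI. For markedly non-normal scales, keep a rank-based or baseline-adjusted rank analysis as a sensitivity check.

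Restrict the paired t and Wilcoxon signed-rank tests to comparisons of time points within patients, label them descriptive, and replace the between-groups wording. Name the overall test as repeated-measures ANOVA with Greenhouse-Geisser correction, or Friedman. Run the pairwise tests only after that test is significant, or apply a Holm correction. State that the effect of the care protocol is not to be judged by setting one arm's within-arm p-value against the other's.

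**Cost.** No new data are needed. The change is to the wording of the plan plus slightly more analysis work. Because the document is written in the past tense, it may mean re-running analyses already done. Some within-arm pairwise results will become slightly less favourable.
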